### Research Synopsis

Study title - Rapidly absorbing polyglactin 910 versus monocryl for laceration repair: a randomized trial

Study Population – recently postpartum women who delivered at Virginia Commonwealth University Labor and Delivery with a first or second degree laceration or episiotomy requiring repair

Study Design – Prospective, randomized

Sample Size – 400

Study Duration – 24 months

Primary Objective – dyspareunia

Secondary Objectives – perineal pain

### Background and Significance

Obstetric perineal trauma is a worldwide problem impacting approximately 85% of women having vaginal deliveries with at least two-thirds requiring perineal repair. The associated pain and discomfort can have a great impact on a woman in the immediate post partum time period while she adjusts to the demands of caring for a newborn. Not uncommonly this pain can persist for several months and 20% may experience long-term problems with persistent pain and dyspareunia. It is important to minimize the negative effects of perineal lacerations by choosing the correct suture material and using the proper technique to reapproximate the anatomy.

Sutures are used to close the wound, minimize bleeding, prevent infection and promote healing. Various sutures have been used to reapproximate perineal lacerations. The ideal suture choice would have minimal tissue reactivity and be absorbed once the wound has healed to prevent tissue scarring and inflammatory reaction. Suture that remains in place longer than needed may impair healing leading to wound infection and breakdown or scarring with subsequent pain. A variety of suture materials have been used to close perineal lacerations, including catgut, absorbable braided and monofilament materials, and newer rapidly absorbed braided material.

Catgut suture is made from collagen derived from the intestines of sheep and cows and is reported to cause an increased inflammatory response in the tissues due to the fact that it is broken down by proteolytic enzymes and phagocytosis (Irvin 1981). Chromic catgut suture is treated with chromate salts to slow down the absorption process and decrease the inflammatory response. A Cochrane review of 18 RCTs compared absorbable synthetic suture to chromic catgut for perineal repair and found that absorbable synthetic material significantly reduced short-term perineal pain, analgesia use within 10 days, rates of suture dehiscence and resuturing compared with catgut. However, there were no clear differences in long-term pain and dyspareunia.

Common synthetic absorbable sutures used in laceration repair include polyglycolic acid, polyglactin 910, and monofilament poliglecaprone 25. Both polyglycolic acid and polyglactin 910 are braided sutures. Polyglycolic acid is designed to be absorbed by the body in 120 days and polyglactin 910 is usually absorbed by 90 days. Both sutures are similarly designed to reduce bacterial adherence and

tissue drag. Monofilament suture is also designed to have reduced tissue drag and minimal tissue reaction. It is absorbed from the body in 90 to 110 days.

A more recent type of polyglactin 910 is now being commonly used in perineal laceration repair. This more rapidly absorbable material is identical to standard polyglactin 910 in chemical composition but due to change in the manufacturing process, is absorbed in less time. This suture is completely absorbed by the tissue in 42 days compared to 90 days with standard polyglactin 910. This more rapid absorption is presumed to promote wound healing with less scarring and inflammatory response.

The 2010 Cochrane systematic review of absorbable suture material for perineal repair included comparisons of standard sutures with rapidly absorbing synthetic (five trials) and monofilament sutures (one trial). In the comparison of standard synthetic with rapidly absorbing sutures, short- and long-term pain were similar. One trial found those with rapidly absorbing sutures required less analgesics at 10 days. More women with standard synthetic suture required suture removal compared to the rapidly absorbed group. There was no evidence of significant difference between groups for long-term pain or dyspareunia. The one trial comparing monofilament with standard polyglycolic suture found no difference for most outcomes. There have been no studies to date comparing rapidly absorbable suture to monofilament.

The purpose of this study is to compare monofilament suture with the rapidly absorbing polyglactin 910. We will compare pain, rate of dyspareunia, and overall sexual function.

#### Objectives:

##### Primary Objective

To evaluate the rates of dyspareunia using a female sexual function index -6 survey with rapidly absorbing polyglactin 910 compared to monocryl.

##### Secondary Objectives

To assess overall perineal pain using a pain scale.

To assess overall sexual function.

#### Study design/methodology:

This randomized controlled trial will be conducted at VCU medical center comparing 2 types of suture: rapid polyglactin 910 (Vicryl Rapide) and monofilament (Monocryl) for first and second-degree lacerations or uncomplicated episiotomies requiring suture repair. Patients will be enrolled in the study immediately after vaginal delivery if a laceration occurs spontaneously or if episiotomy is performed. Patients will be randomized to one of the 2 sutures after enrollment. Inclusion criteria include English speaking, patients with first and second degree spontaneous lacerations or those with midline or mediolateral episiotomies that were uncomplicated, and hemodynamically stable patients. Exclusion criteria include non-english or Spanish speaking, women without laceration or with third or fourth degree lacerations.

Randomization will be obtained via computer generation in consecutively numbered, opaque sealed envelopes with the name of one of the suture materials. The envelope will be opened at the time of repair of perineal laceration once inclusion criteria have been met by the physician or midwife performing the laceration repair. Repair with the chosen suture will be performed using the continuous suture technique using a 3-0 suture. Various maternal and fetal characteristics will be recorded

including maternal age, gravity and parity, gestational age at delivery, birth weight, insurance type and race.

In the immediate postpartum time period while the patient is hospitalized, patients will be given ibuprofen 600 mg every 6 hours or oxycodone 5mg and acetaminophen 325mg every 4 hours as needed for pain. If sufficient pain control is not achieved with these medications, then morphine 4mg IV will be administered until appropriate pain control is satisfactory. They will also be give the standard prescriptions that are routinely dispensed to all postpartum patients including ibuprofen 600mg every 6 hours and oxycodone 5mg and acetaminophen 325mg every 4 hours to be used as needed.

Pain will be evaluated using a pain scale at 6 week telephone interview. At three months postpartum another telephone interview will be conducted and six questions of the Female Sexual Function Index will be asked.

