#### Informed Consent Process:

Informed consent will be obtained after delivery, prior to laceration repair.

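### The plan has no provision to keep women or telephone interviewers unaware of the suture, although every outcome is self-reported by telephone

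*Combined protocol and SAP*

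**What the plan says.** The Research Synopsis labels the design only as "Study Design – Prospective, randomized". The words blind, masked and open-label do not appear in it or in the rest of the text.

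Study design/methodology describes the allocation as computer-generated and held in "consecutively numbered, opaque sealed envelopes with the name of one of the suture materials". On timing it says "The envelope will be opened at the time of repair of perineal laceration", and it continues "once inclusion criteria have been met by the physician or midwife performing the laceration repair". The operator therefore knows the suture from that moment. Under Informed Consent Process, "Informed consent will be obtained after delivery, prior to laceration repair", so the woman has been approached about the study before the envelope is opened.

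The primary objective is "To evaluate the rates of dyspareunia using a female sexual function index -6 survey". The secondary objectives are perineal pain on a pain scale and overall sexual function. Two calls collect these outcomes:

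- 6 weeks: "Pain will be evaluated using a pain scale at 6 week telephone interview".
- 3 months: "At three months postpartum another telephone interview will be conducted and six questions of the Female Sexual Function Index will be asked".

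The plan does not say who makes the calls, what the callers can see, or what the woman is told about her suture.

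**The concern.** Sealed opaque envelopes protect the assignment up to the moment they are opened. They do nothing for how outcomes are reported or elicited afterwards. Here all the outcomes are subjective, all are obtained by one person questioning another, and no objective endpoint is planned as a cross-check.

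The operator cannot practically be masked, because the two materials are different sutures handled directly. The woman and the caller can be. If they are not, a woman who knows her suture, or a caller who knows it (possibly the clinician who placed it), can influence the answers differently in the two arms. A difference produced that way cannot be separated from a suture effect in the analysis, so protection has to be in place before the calls begin.

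**Working it through.** **Step 1. What the documents provide at each point where knowledge of the suture could enter.**

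| Person | What the plan says | Provision to keep unaware |
|---|---|---|
| Operator | Opens the envelope at the repair | None practicable |
| Woman | Consents before the repair; nothing on what she is told afterwards | None stated |
| Caller | Telephones at 6 weeks and 3 months; role and access to the allocation not stated | None stated |

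Two other passages might be thought to fill the gap. The Privacy section password-protects the names and links them to a study number, but it does not separate the allocation from the list used for calling. The six FSFI items are set questions, which limits improvisation at 3 months, but they do not mask the person asking, and nothing similar is described for the 6-week pain call.

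**Step 2. Inputs for a sensitivity calculation.**

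- From the Statistical Analysis Plan: 200 per arm, 15% loss, SD 1, pain difference sought 0.25. Evaluable per arm: 200 × 0.85 = 170.
- From Background: 20% is given for long-term problems with persistent pain and dyspareunia. It is used here as an assumed dyspareunia rate; the plan states neither an expected rate nor a target difference.
- Assumed because not stated: two-sided 5% test.
- Size of the reporting shift: not in the documents, so it is only varied.

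**Step 3. The plan's own figure.** The detectable difference is (z_alpha + z_power) × SD × √(2/n). Power and sidedness are not stated, so 0.25 cannot be strictly reproduced. At 80% power:

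| n per arm | Two-sided 5% | One-sided 5% |
|---|---|---|
| 200 | 0.280 | 0.249 |
| 170 | 0.304 | 0.270 |

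Of these four, only the one-sided figure with the loss ignored comes to 0.25. That is a separate matter; 0.25 serves here only as the yardstick for the effect sought.

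**Step 4. Pain.** Suppose there is no true difference and the observed difference is entirely a reporting shift b. The standard error is √(2/170) = 0.1085. The rejection probability is Φ(b/0.1085 − 1.96) + Φ(−b/0.1085 − 1.96). For b = 0.10, b/SE = 0.922, which gives 0.1496 + 0.0020 = 0.152.

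| Shift b | False-positive rate |
|---|---|
| 0 | 5.0% |
| 0.05 | 7.5% |
| 0.10 | 15.2% |
| 0.15 | 28.2% |
| 0.20 | 45.4% |
| 0.25 | 63.5% |

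The last row is the power of the same test at 0.25, as it must be. It says nothing about how likely such a shift is.

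**Step 5. Dyspareunia.** This is an exact enumeration of two binomials, 170 per arm, with the Pearson chi-square test. One arm is at 20% and the other is shifted by reporting alone, upward or downward.

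| Shift | False-positive rate |
|---|---|
| 0 | 5.1% |
| 3 points | 10.5% (up), 11.1% (down) |
| 5 points | 19.9% (up), 23.0% (down) |

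**The case against.** The strongest reply is that silence is not evidence of unmasked conduct. No sentence says that women are told their suture, that callers see the allocation, or that the repairing clinician makes the call. The consent pages are not in the text available, so what women are told cannot be judged. This stands: a reader might infer that the trial is declared or run as open-label, and the documents do not support that. It does not dispose of the point, because the protocol as written still permits unmasked elicitation, and consent wording would not control who calls or what the caller sees.

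A reader might also infer that the bias is as large as the effect sought. The documents give no size for any bias. For the primary outcome they give no target difference to compare it with. At the assumed 20% rate, 80% power with 170 per arm needs a fall of about 10.8 points or a rise of about 13.4, so the 3- and 5-point shifts above are half of that or less.

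Nor can the direction be inferred. Background presumes that faster absorption means better healing with less scarring and inflammation, but it also credits monofilament with minimal tissue reaction. It reports similar short- and long-term pain for standard and rapidly absorbing sutures, and no earlier comparison of the rapid suture with monofilament. Nothing shows that women are given the investigators' presumption.

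Finally, some safeguards exist: both arms receive an absorbable suture of the same size placed with the same technique, the FSFI items are fixed, and names are linked to a study number. These limit other differences between arms, but none of them masks the woman or the caller.

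**Conclusion.** The point holds as a gap in the design. The plan has no provision for masking women or callers, while all its outcomes are self-reports taken by telephone. Followed as written, nothing prevents an informed woman or caller from influencing the answers.

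The figures show how sensitive the trial would be, not how biased it is. A pain shift of 0.10, which is 40% of the 0.25 sought (0.10/0.25), would about triple the false-positive rate, from 5% to 15%. A 5-point dyspareunia shift would take it to about 20–23%. Both rest on 170 evaluable women per arm, a two-sided 5% test and no true difference; the first also rests on SD 1 and the second on an assumed 20% rate. The size and direction of any actual bias are unknown. The change is worth making because it uses calls already planned and alters neither the sample size nor the interventions compared.

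**What to change.** Add to Study design/methodology:

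1. The suture type is not volunteered to the woman until her 3-month call is complete. Disclosure is allowed at any time if she or a treating clinician needs it.
2. The allocation is kept apart from the call list; callers see only the study number and contact details.
3. Nobody who performed or assisted at a repair telephones that woman.
4. Both calls, including the 6-week pain question, follow a fixed script.
5. At the end of the 3-month call, the caller records whether the woman or the caller knows the suture.

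The cost is protocol wording, splitting one data file, and assigning calls so that they avoid the repairing clinician. The woman also learns her suture type later than she otherwise might. The documents do not describe staffing, so whether a separate caller is always available must be confirmed locally.

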#### Study Population:

Inclusion criteria include English speaking patients with first and second degree spontaneous lacerations or those with midline or mediolateral episiotomies that were uncomplicated, and hemodynamically stable patients.

Exclusion criteria include non-english speaking women without laceration or with third or fourth degree lacerations.

#### Study Duration/ Study Timeline:

Stage 1 – Enrolling patients and randomization

Stage 2 – follow up at 6 weeks and 3 months

Stage 3 – data analysis

Stage 4 – presentation and publication

Projected start date: 8/2014

Total length of time: 36 months

Approximate end date: 8/2017

#### Statistical Analysis Plan:

A chi square analysis and Fisher's exact test will be used for data analysis.

A goal sample size of 400 patients will be included in the study. With 200 patients in each arm of the study and assuming a standard deviation of 1, with a 15% loss to follow up, we would be able to detect a difference in pain scores of 0.25 or more.

Patients will be excluded from analysis if they are lost to follow up after the repair. Attempts will be made to contact the patient via telephone. If the patient is lost to follow up after their 6 week visit, this data will be included in the analysis.

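### The only tests named compare category counts, but the 400 patients are justified by a difference in mean pain score, and neither a test for scores nor a pain cut-point is fixed

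*Combined protocol and SAP*

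**What the plan says.** The whole statement on tests, in the Statistical Analysis Plan section, is "A chi square analysis and Fisher's exact test will be used for data analysis". Neither test is tied to an outcome.

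The next paragraph bases the sample size on 200 patients per arm, 15% loss to follow-up and "assuming a standard deviation of 1", and concludes that "we would be able to detect a difference in pain scores of 0.25 or more". Significance level, sidedness and power are not stated.

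The outcomes are described elsewhere:

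- **Dyspareunia (primary).** The Primary Objective is "To evaluate the rates of dyspareunia using a female sexual function index -6 survey".
- **Pain (secondary).** The objective is "To assess overall perineal pain using a pain scale". Under Study design/methodology, "Pain will be evaluated using a pain scale at 6 week telephone interview". The scale is not named and its range is not given.
- **Sexual function (secondary).** The objective is "To assess overall sexual function". At three months, "six questions of the Female Sexual Function Index will be asked". No scoring rule is given.

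No section names a t-test, rank test, trend test or model, and none sets a cut-point for pain.

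**The concern.** The plan's only quantitative target is a difference in mean pain score, yet its only named tests do not compare means. If they are applied to the pain score as written, one of two things has to happen. The score is dichotomised at a cut the plan does not give, or every score value becomes a column of an unordered table that ignores the ranking of the scores. Neither yields an estimate in the units of the planned 0.25.

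Two things are at stake. The trial would report pain in a form that cannot be set against its own sample-size basis. And with test and cut both open, they can be chosen once the data are visible, and that choice can decide the result.

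A related gap touches the primary outcome. A chi-square test suits a rate of dyspareunia, but no section says which FSFI-6 response makes a woman a case. That cut is open too.

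**Working it through.** **1. Inputs.** From the Statistical Analysis Plan section: 200 per arm, 15% loss, SD 1, difference 0.25. Evaluable patients: 200 × 0.85 = 170 per arm. Assumed, because not stated: two-sided 5%, and 80% power where a power is needed. The score shapes below are also assumed.

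**2. The plan's own figure.** Detectable difference = (z_alpha + z_power) × SD × √(2/n).

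- n = 170, two-sided 5%, 80% power: (1.960 + 0.842) × √(2/170) = 2.802 × 0.1085 = 0.304.
- n = 200, one-sided 5%, 80% power: (1.645 + 0.842) × √(2/200) = 2.487 × 0.1 = 0.249.

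Of the settings tried (one- or two-sided 5%, 80% or 90% power, 170 or 200 per arm), only the second gives 0.25, and it ignores the loss. That is a separate matter. What counts here is that the calculation has the form of a comparison of two means.

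**3. Power at 0.25, normal scores, 170 per arm.**

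- t-test: noncentrality 0.25 × √(170/2) = 2.305. The normal approximation gives Φ(2.305 − 1.960) = 0.635, and the noncentral t gives 0.632.
- 2x2 chi-square: power = Φ{[|p2 − p1|√n − 1.96√(2p̄(1 − p̄))] / √(p1(1 − p1) + p2(1 − p2))}, where p1 and p2 are the proportions above the cut.
  - Cut at the median of the lower arm: 0.500 against 0.599, power 0.448.
  - Cut 1 SD above it: 0.159 against 0.227, power 0.355.

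**4. Power at about 0.25, other shapes (simulation).**

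| Assumed shape | t-test | 2x2, any pain | 2x2, score above 2 |
|---|---|---|---|
| Many zeros: any pain 20% v 32.5% | 63% | 75% | 25% |
| Any pain 40% in both arms, severity differs | 53–55% | 5% | 87% |

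In both rows one cut beats the t-test and the other falls far below it. In the second row a single unordered table also beats the t-test (86%). The t-test moves least, because it depends mainly on the difference and the SD, the two figures the plan gives.

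**5. False positives with no true difference, 170 per arm (simulation).** Shapes: rounded normal on 0–10, and scores with any pain in 20%, 32.5% or 40%.

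- One cut fixed in advance: about 5%.
- One unordered table of all categories, sparse ones merged: 4.7–4.9%.
- Most favourable of all cuts, Fisher's exact test: 7.3–12.4%.
- Most favourable of all cuts with expected counts of at least 5, uncorrected chi-square: 11.7–16.8%.

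A second set of shapes with SD about 0.9–1.04 gave about 9–12% with Fisher and 12.5–16.6% with chi-square plus Fisher for small cells. Uncorrected chi-square at every cut, sparse ones included, reached 19.4% in one of these. Wider scores (SD about 1.4–3.2) gave about 16–27% with the chi-square-plus-Fisher rule.

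**The case against.** The strongest reply is that the benign reading is also the natural one. A difference in scores set against an SD implies a comparison of means, and the one-line list of tests is simply incomplete for a secondary outcome. Nothing says that scores will be cut. This stands as far as intent goes. But the sentence naming the tests covers the data analysis without exception, and a test that is not written down is not pre-specified.

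A second reply is that the named tests are not inferior. This stands too: step 4 shows them ahead of the t-test in both skewed scenarios. A reader might infer that categorical tests cost power in general. The documents give no score distribution, so they do not support that.

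A reader might also infer that the plan carries a false-positive rate of 12–17% for pain. It does not. That range needs dichotomisation, a search over all cuts after the data are seen, chi-square rather than Fisher alone, and particular score shapes, none of which the documents state. One unordered table would keep the rate near 5%.

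Finally, because pain is secondary, a reader might conclude that the primary comparison is safe. The choice of test for the dyspareunia rate is sound, but the definition of a case is missing, so the documents do not support that conclusion either.

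**Conclusion.** The point holds as a mismatch and a failure to pre-specify. The plan's stated tests cannot estimate the difference on which its 400 patients rest, and no test for scores or pain cut-point is fixed. This follows from the text alone and needs no assumption.

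The sizes are illustrative and rest on two-sided 5%, 170 per arm and assumed score shapes. For normal scores, power is 63% by t-test against about 35–45% by 2x2 chi-square at cuts from the median to 1 SD, but the order can reverse for skewed scores. For SDs near 1, false positives rise from about 5% to roughly 7–17%, depending on Fisher or chi-square, only if the most favourable cut is taken after the fact. They are higher for wider scores.

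It should be fixed. It does not invalidate the chi-square test for the dyspareunia rate, though that rate needs a fixed case definition.

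**What to change.** Amend the Statistical Analysis Plan section before any outcome data are examined:

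- **Dyspareunia rate:** keep chi-square, with Fisher's exact test when an expected count is below 5. State which FSFI-6 response counts as dyspareunia.
- **Pain at 6 weeks:** name the scale and its range. Make a two-sample comparison of means the main analysis, reported as mean difference with 95% CI. Always report a Wilcoxon rank-sum test as a fixed sensitivity analysis, since scores may be skewed or mostly zero.
- **Proportion with pain, if wanted:** fix the cut-point now and label the analysis supportive.
- **Sexual function:** state how the FSFI-6 summary score is computed and analyse it in the same way as pain.

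The cost is a few sentences, with no new data or visits. The downside is statistical: the comparison of means may have less power than a categorical one if most scores are zero (63% against 75% in the scenario above) or if the arms differ only in severity (53–55% against 87% at the best cut).

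### The 0.25 pain-score difference has no stated alpha, sidedness, power or test of means; at 5% and 80% power it holds only one-sided with the 15% loss ignored

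*Combined protocol and SAP*

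**What the plan says.** The Statistical Analysis Plan section sets a goal of 400 patients and justifies it in one sentence. Its premises are "With 200 patients in each arm of the study and assuming a standard deviation of 1", and its conclusion is that "with a 15% loss to follow up, we would be able to detect a difference in pain scores of 0.25 or more". No alpha, sidedness or power is given there or anywhere else in the document.

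On analysis, the section says: "A chi square analysis and Fisher's exact test will be used for data analysis". No other test is named.

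On missing patients, it says: "Patients will be excluded from analysis if they are lost to follow up after the repair". It adds: "If the patient is lost to follow up after their 6 week visit, this data will be included in the analysis".

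Pain is a secondary outcome: "To assess overall perineal pain using a pain scale" (Secondary Objectives). Its timing is in Study design/methodology: "Pain will be evaluated using a pain scale at 6 week telephone interview". The scale is not named. The primary objective is different: "To evaluate the rates of dyspareunia using a female sexual function index -6 survey" (Primary Objective).

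**The concern.** A detectable difference means something only with an alpha, a sidedness and a power attached. Here all three are missing, so a reader cannot check the one figure offered in support of 400 patients. A standard deviation and a score difference imply a comparison of means, yet neither named test makes one. The scale is unnamed, so the SD of 1 and the 0.25 have no units.

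The sentence also presents the 15% loss as already allowed for. Lost patients are removed from the analysis, so the loss lowers the number analysed, and the usual settings then do not give 0.25.

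What is at stake is how a null pain result would be read. Under a two-sided 5% test, a true difference of 0.25 SD would be missed 37% of the time with 170 analysed per arm and 30% of the time with 200. The plan's wording conveys neither.

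**Working it through.** **Inputs from the Statistical Analysis Plan section:** 200 per arm, SD 1, difference 0.25, loss 15%. Analysed per arm if the loss applies in full: 200 × (1 − 0.15) = 170.

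**Assumed, because the plan is silent:** a two-sample comparison of means at alpha 5%, one- or two-sided, with 80% power as the main case.

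**Formulas (normal approximation):**

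- detectable difference = (z_alpha + z_power) × SD × √(2/n)
- power = Φ(0.25 / (SD × √(2/n)) − z_alpha)
- n per arm = 2 × (z_alpha + z_power)² × SD² / 0.25²

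Here z_alpha is 1.645 one-sided or 1.960 two-sided, and z_power is 0.842 for 80%.

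**Reproducing the plan's figure.** With n = 200, √(2/200) = 0.100. One-sided 5% at 80% power gives (1.645 + 0.842) × 0.100 = 0.249, which matches 0.25. No loss has been applied.

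**Applying the loss.** With n = 170, √(2/170) = 0.1085.

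- One-sided: 2.487 × 0.1085 = 0.270. Power for 0.25 is Φ(2.305 − 1.645) = 74.5%.
- Two-sided: 2.802 × 0.1085 = 0.304. Power for 0.25 is Φ(2.305 − 1.960) = 63.5%.

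**The same quantities from the noncentral t distribution (df = 2n − 2), which are the figures used below:**

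| Analysed per arm | Test at 5% | Power for 0.25 | Detectable at 80% power | Detectable at 90% power |
|---|---|---|---|---|
| 170 | two-sided | 63% | 0.305 | 0.353 |
| 170 | one-sided | 74% | 0.270 | 0.318 |
| 200 | two-sided | 70% | 0.281 | 0.325 |
| 200 | one-sided | 80% | 0.249 | 0.293 |

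**How much loss the matching case tolerates.** One-sided 5% at 80% power for 0.25 needs 199 analysed per arm by the t test (198 by the normal approximation). The loss allowed from 200 is 1/200 = 0.5%.

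**What would rescue 0.25 at 170 per arm and 80% power.** Either a two-sided alpha of 0.144, or a smaller SD: 0.25/0.3047 = 0.82 for two-sided 5%, or 0.25/0.2702 = 0.925 for one-sided 5%.

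**Other settings that match or come close:**

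- One-sided 10% with 170 per arm gives 85% power.
- Two-sided 10% at 80% power is the same calculation as one-sided 5%, so it also needs the loss ignored.
- Two-sided 5% at 70% power needs 198 per arm by the normal approximation, again with the loss ignored.
- One-sided 5% at 75% power needs 173 analysed per arm (normal approximation), just above 170.

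**The case against.** The strongest reply is that alpha and power are not in the document, so no figure can be shown to be wrong. One-sided 10% with 170 per arm supports 0.25 comfortably. That stands, and it limits the conclusion: the omission is certain, but the numerical shortfall is conditional on 5% and 80%.

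A second reply is that 170 is itself an assumption. The plan does not say when the 15% occurs, pain is asked at 6 weeks, and data from patients lost later are kept. The number analysed for pain could therefore lie anywhere from 170 to 200 per arm. This also stands, and one-sided the gap is then at most 8% (0.270 against 0.25). It does not rescue the conventional reading: two-sided 5% at 80% power misses 0.25 even with all 200.

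Third, 200 might mean patients remaining after loss. Enrolment would then have to be about 200/0.85 = 235 per arm, or 470 in total, against the stated goal of 400.

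Fourth, pain is secondary, and the absence of any calculation for dyspareunia matters more. That is fair. Correcting this sentence will not supply that calculation.

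Lastly, a t test may not suit an unnamed and possibly ordinal scale, and the mid-point analysis under Data Safety Monitoring would change these figures if it tested pain and spent alpha. The plan describes that look as a safety check, so this is only a possibility.

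**Conclusion.** The concern holds. Alpha, sidedness, power and a test of means are all absent. At 5% with 80% or 90% power, the stated 0.25 is reproduced only one-sided (equivalently two-sided 10%), at 80% power, with essentially none of the 15% loss applied.

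Under two-sided 5% at 80% power, the detectable difference is 12% to 22% above the stated value (0.281 with 200 analysed per arm, 0.305 with 170). This rests on a two-sample comparison of means, SD 1 and equal arms.

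The figure is incompletely specified and optimistic under conventional settings; it is not a proven arithmetic error. The effect is confined to the secondary pain outcome.

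**What to change.** Keep the goal of 400 patients. In the Statistical Analysis Plan section:

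1. State the alpha, sidedness and power, and the time point to which the 15% loss applies.
2. Restate the detectable difference to match. If two-sided 5%, 80% power and 170 analysed per arm at 6 weeks are intended, suitable wording is: *With 170 per arm analysed, a two-sample t test of mean pain scores at two-sided 5% has 80% power to detect a difference of 0.305 SD; power for 0.25 SD is 63%.* If one-sided 5% is intended, say so and give 0.270 SD at 80% power and 74% power for 0.25 SD.
3. Add the chosen comparison of mean pain scores to the methods beside chi-square and Fisher's exact test. If the team prefers a rank or categorical comparison, base the restated figure on that method.
4. Name the pain scale, so that the SD and the difference have units.

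The cost is one restated sentence, one added test and one named scale, with no extra patients or visits. The stated detectable difference becomes slightly less favourable. Holding 0.25 at two-sided 5% and 80% power would instead need 252 analysed per arm (normal approximation), or 252/0.85 = 297 enrolled per arm and 594 in total. That is not proposed for a secondary outcome.
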